3.3 Exploratory Objective

- (1) Objective: To identify predictive biomarkers to pembrolizumab and lenvatinib which correlate with intracranial and extracranial responses and toxicity via a combination of immunohistochemical, transcriptional, protein, and genetic assays using pre-treatment tumor and pre- and on-treatment blood samples.

Hypothesis: Analysis of patient samples will identify useful biomarkers to help determine, at baseline, patients who will respond or who will experience toxicity from combination pembrolizumab and lenvatinib.

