7.1.2.10.3 Correlative Studies

Correlative studies will be conducted on the pre-treatment tissue specimen. A number of additional biomarkers will be studied for their potential predictive value in pre-treatment CNS specimens taken at the time of surgery or LITT and/or on tumor tissue from a systemic site. These exploratory studies include (but are not limited to):

- 1) Markers to be studied on tumor cells: B7H1, PDL2, B7H4, Galactin-9.
- 2) Percent of tumor sample that constitutes CD4 and CD8 cells
- 3) Markers on T cells: LAG-3 on CD4 cells, PD1-H (PD-1 homologue) on T cells, CTLA4 on T cells TIM3 on T cells

Patients who undergo surgical procedures (either of the CNS or peripheral) while on systemic treatment will also be asked to provide a research specimen to determine changes in the above markers in the context of response or resistance to therapy.

Levels of all of the above markers will be measured by a method of Automated Quantitative Analysis (AQUA) of in situ protein levels in [name] laboratory at Yale University. This method has been validated for epithelial cancers and melanoma and has shown to be more precise than pathologist-based scoring of 3,3'-diaminobenzidine stain. AQUA is highly reproducible and quantitative, as reviewed (Jilaveanu et al., 2009). Tumors will be stained with a number of fluorophores: A tumor mask for melanoma will be made using a cocktail of anti-S100 and anti-Melan-A. The methods for masking tumor have been described in the literature (Berger et al., 2004; Camp, Chung, & Rimm, 2002; Kluger et al., 2008). The mask will be conjugated to Cy-3, and will be differentiated from the target antigen, which will be conjugated to Cy-5. After fluorescent staining is completed, images are taken at the different wavelengths, and the images will be analyzed using algorithms that have been extensively described 58. A monochromatic, high-resolution images of each histospot will be obtained using the 10 \times objective of an Olympus AX-51 epifluorescence microscope (Olympus) with automated microscope stage and digital image acquisition driven by a custom program and macrobased interfaces with IPLabs software (Scanalytics, Inc.). Tumor will be distinguished from stromal elements by the tumor mask signal. The signal intensity of the target biomarker will be scored on a scale of 0-255 (the AQUA score). This will provide quantitative results.

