Biomarker analysis will be conducted using standard methods. Associations between continuous AQUA scores and binarized outcome variables (such as response) will be done by ANOVA. Cox univariate analysis will be used to study the associations between the survival endpoints and biomarker expression; Kaplan Meier curves will be generated to depict the association between binarized biomarker levels and survival endpoints. Multivariable models will be generated to predict response.

Immune monitoring will be performed as a part of this study. Peripheral blood lymphocytes (PBLs) and plasma (approximately 40cc) will be collected before cycles 1, 2, and 3, and subsequent to that, before every 3rd cycle thereafter, until patients come off of study. PBMCs will be separated and cryopreserved for T and B cell studies. Samples will be stored for immunophenotyping studies and serological profiling to be done using the Yale Cy-TOF core facility, or flow cytometry and by Eve Technologies.

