All subjects will be included in the safety analysis. Incidence tables will be generated to summarize incidence of patients reporting at least one episode of each specific adverse event, incidence of adverse events causing withdrawals and incidence of serious adverse events. Listing of adverse events by patients will include the time to onset, the duration of each event, the severity of each event, and the relationship of the event to study therapy, whether it was a serious event, and whether it caused withdrawal.

Exploratory Objectives

Biomarker Studies

Immunohistochemical evaluation of baseline tumor PD-L1 staining, TIL populations, and other immune and angiogenic factors that may predict tumor sensitivity to this drug combination will be compared between non-responders (SD and PD) versus responders (PR and CR) using a mixed methods approach, that adjusts for repeated measures over time and response as defined above. If there are differences by time, pairwise contrasts will be utilized to assess for specific differences at various time points, adjusting for multiple comparisons using the Tukey method.

For patients who have on-treatment tumor samples, comparison will be made to pre-treatment tissue for PD-L1 staining, TIL populations, and other immune and angiogenic factors that may predict tumor sensitivity. Differences in these markers by response will be assessed using two-sample t-test.

Blood samples collected before and on treatment will be analyzed for cytokines and by flow cytometry. Data will be analyzed by a repeated measures ANOVA and adjusted for multiple comparisons via Tukey method.

TIL will be extracted from resected pre-treatment specimens and subjected to immunophenotyping studies to characterize T and B cells using single-cell RNA-sequencing. Data will be analyzed by a repeated measures ANOVA and adjusted for multiple comparisons via Tukey method.

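### The Tukey adjustment stated for the blood and TIL sequencing data does not cover multiplicity across cytokines, cell populations or genes, although the text reads as if it did

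*Combined protocol and SAP*

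**What the plan says.** Section 8.3, under Exploratory Objectives, names Tukey in three places.

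- **Tissue immunohistochemistry:** if markers differ by time, "pairwise contrasts will be utilized to assess for specific differences at various time points, adjusting for multiple comparisons using the Tukey method". This is the only sentence that says what Tukey is applied to.
- **Blood cytokines and flow cytometry:** "Data will be analyzed by a repeated measures ANOVA and adjusted for multiple comparisons via Tukey method".
- **TIL single-cell RNA-sequencing:** the same sentence again, for TIL taken from resected pre-treatment specimens.

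Other biomarker tests state no adjustment. For patients with on-treatment tissue, Section 8.3 says "Differences in these markers by response will be assessed using two-sample t-test". Section 7.1.2.10.3 says "Associations between continuous AQUA scores and binarized outcome variables (such as response) will be done by ANOVA" and "Cox univariate analysis will be used to study the associations between the survival endpoints and biomarker expression".

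Section 4.2.3.2 says that blood from one later time point will be compared with baseline for a panel of cytokines. The panel size is not given. The same section allows genome-wide expression profiling, with no gene count and no multiplicity method.

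The objective is labelled exploratory, but its hypothesis in Section 3.3 is firm: "Analysis of patient samples will identify useful biomarkers to help determine, at baseline, patients who will respond or who will experience toxicity". I found no biomarker significance level, family of markers, false-discovery rate, lead marker or validation step.

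**The concern.** In multi-analyte work the multiplicity lies mainly across analytes: many cytokines, many cell populations, possibly thousands of genes. Tukey's method controls error over pairwise mean differences within one ANOVA, that is, for one analyte at a time. An analyst who follows Section 8.3 to the letter could call a cytokine or gene significant after adjustment for multiple comparisons, although no account had been taken of how many cytokines or genes were tested.

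At stake is the credibility of any marker put forward as a baseline predictor of response or toxicity. A plainly unadjusted exploratory p-value warns the reader. A p-value described as adjusted, when the adjustment did not touch the relevant family, does not.

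**Working it through.** The plan states no error rate or number of tests for the biomarkers, so there is no figure of its own to reproduce. The check has two parts.

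**1. What Tukey does in the two places where the sentence is used**

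Tukey compares each pairwise difference with a critical value q(k, df)/√2, where q is the studentized-range quantile and k is the number of means. For k = 2 this equals the two-sided t quantile. With df = 26 (27 patients, two time points), both are 2.056. In a two-group example the Tukey and t-test p-values were both 0.586.

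- *Blood.* Section 4.2.3.2 compares baseline with one later sample, so k = 2 and there is one contrast. Tukey adjusts nothing. If response were crossed with time (four cell means, six pairwise contrasts), Tukey would adjust those six, but still within one cytokine.
- *TIL sequencing.* The specimens are pre-treatment, so there is no repeated time point. Responder against non-responder is again k = 2. If some other repeated factor is meant, such as cell type, the plan does not say so, and the adjustment would still be within one gene.

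A null simulation (27 patients, 2 or 4 time points, Tukey at 5% within each marker, 1,500 runs) shows the consequence. Error for a single marker was 4.5–5.4%, as intended. The chance of at least one false marker was:

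| Markers | Independent | Correlation 0.5 |
|---|---|---|
| 10 | 39–40% | 31–32% |
| 40 | 87% | 57–59% |

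The counts 10 and 40 are illustrative here, because the plan gives no count for the blood or TIL assays.

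**2. The tests that state no adjustment**

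The only marker count in the documents is in Section 7.1.2.10.3:

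- four tumour-cell markers ("Markers to be studied on tumor cells: B7H1, PDL2, B7H4, Galactin-9");
- two cell percentages ("Percent of tumor sample that constitutes CD4 and CD8 cells");
- four T-cell markers (LAG-3, PD1-H, CTLA4, TIM3).

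The total is 4 + 2 + 4 = 10, and the list is open-ended. Assume one test per marker at two-sided 0.05; that threshold is my assumption.

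- Independent tests: 1 − 0.95^10 = 1 − 0.599 = **0.40**. Expected false positives: 10 × 0.05 = 0.5.
- Equal correlation 0.5 between markers: **0.29** for normal test statistics, and 0.31–0.32 in the small simulation above, so about 0.3.
- Equal correlation 0.8: 0.17.

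Independent tests pass one half at 14: 1 − 0.95^13 = 0.487 and 1 − 0.95^14 = 0.512.

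**3. After a correction across the ten markers**

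- Bonferroni at 0.05/10 = 0.005 gives 1 − 0.995^10 = 0.049 if independent. Take an assumed 5 responders against 22 non-responders (0.20 × 27 = 5.4, using the melanoma target rate) and an assumed standardised difference of 1.5. Power for one marker then falls from 83% at 0.05 to 49% at 0.005.
- Benjamini-Hochberg at level q holds the chance of any false hit at q when all ten markers are null and independent. It rejects everything that Bonferroni rejects at the same level, so its loss of power is no larger.

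**The case against.** The strongest reply is that this work is exploratory and labelled so in Sections 3.3, 7.1.2.10.3 and 8.3. Section 4.2.3.2 is tentative about what may be found. No eligibility, stopping or go/no-go rule uses a biomarker, and strict family-wise control is not required. All of that stands, and it limits the severity. It does not answer the point, because the text does not present the blood and TIL results as unadjusted. It says that they are adjusted, by a method that cannot reach the family that matters.

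It is also fair to say that Tukey is properly used in the immunohistochemistry paragraph, where it is tied to contrasts between time points. That use is not criticised.

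A reader might infer more than the documents support:

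- **That the 0.40 and 0.3 measure the error behind the Tukey claim.** They belong to the ten tissue markers, whose AQUA tests claim no adjustment. A misdescribed adjustment and an unadjusted test are two separate faults.
- **That hundreds of genes would pass by chance.** No gene count is given, no gene-by-gene test is specified for the TIL data, and genome-wide profiling is only something that may be done.
- **That false predictive markers are likely, or that most hits would be noise.** For the only stated count, the chance of any false hit is below one half. The share of hits that are false also depends on power and on how many markers are truly predictive, and neither is given.
- **That each cohort must be analysed alone with very few responders.** The plan does not say whether the biomarker analyses are by cohort or pooled.

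**Conclusion.** The point holds in a limited form. For blood cytokines, flow cytometry and TIL single-cell RNA-sequencing, the stated Tukey adjustment leaves multiplicity across analytes uncontrolled. In the two-level comparisons that the plan describes, it adjusts nothing. The repeated-measures ANOVA also does not fit pre-treatment TIL. No error rate can be fixed for these assays, because panel size and gene count are not stated.

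Separately, the on-treatment tissue t-tests and the AQUA ANOVA and Cox tests state no adjustment. For the ten named markers tested once each, the chance of at least one false positive is 0.40 if independent and about 0.3 at correlation 0.5. These figures rest on an assumed threshold of 0.05, an assumed correlation, and one test per marker. More outcomes or markers would raise them.

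The primary endpoint and the Simon rules are unaffected. Severity is low to moderate: the wording would mislead, and it is cheap to correct.

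**What to change.** In Section 8.3:

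1. Keep Tukey only for time-point contrasts within a marker, where more than two time points are compared.
2. Replace the repeated-measures ANOVA for pre-treatment TIL with a between-group comparison (responders against non-responders).
3. Add Benjamini-Hochberg false-discovery-rate control across analytes within each assay family and outcome. The families are blood cytokines, cell populations, RNA-sequencing genes, and tissue markers. The last should include the on-treatment t-tests and the AQUA ANOVA and Cox tests of Section 7.1.2.10.3. State the level in advance (for example q = 0.10), and say whether the cohorts are analysed separately or pooled.
4. Report raw p-values beside q-values. Describe any analysis left without this control as unadjusted and hypothesis-generating.

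The level and the grouping into families are choices for the sponsor. Labelling every analysis as unadjusted would also remove the misleading wording, but it would give less protection in the gene-level work.

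The cost is SAP wording and a few lines of code, with no new patients or samples. The downside is fewer nominally significant markers.

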9.0 LABELING, PACKAGING, STORAGE AND RETURN OF CLINICAL SUPPLIES

9.1 Investigational Product

The investigator shall take responsibility for and shall take all steps to maintain appropriate records and ensure appropriate supply, storage, handling, distribution and usage of investigational product in accordance with the protocol and any applicable laws and regulations.

Pembrolizumab and lenvatinib will be provided by Merck as summarized in Table 9.

Table 9 Product Descriptions

Product Name & Potency	Dosage Form
Pembrolizumab 100 mg/ 4mL	Solution for Injection
Lenvatinib 20 mg	Tablet for oral dosing

9.2 Packaging and Labeling Information

Supplies will be labeled in accordance with regulatory requirements.

9.3 Clinical Supplies Disclosure

This trial is open-label; therefore, the participant, the trial site personnel, the Sponsor and/or designee are not blinded to treatment. Drug identity (name, strength) is included in the label text; random code/disclosure envelopes or lists are not provided.

9.4 Storage and Handling Requirements

Clinical supplies must be stored in a secure, limited-access location under the storage conditions specified on the label.

Receipt and dispensing of trial medication must be recorded by an authorized person at the trial site.

Clinical supplies may not be used for any purpose other than that stated in the protocol.

9.5 Returns and Reconciliation

The investigator is responsible for keeping accurate records of the clinical supplies received from Merck or designee, the amount dispensed to and returned by the participants and the amount remaining at the conclusion of the trial.

Upon completion or termination of the study, all unused and/or partially used investigational product will be destroyed at the site per institutional policy. It is the Investigator's responsibility to arrange for disposal of all empty containers, provided that procedures for proper disposal have been established according to applicable federal, state, local and institutional guidelines and procedures, and provided that appropriate records of disposal are kept.

10.0 ADMINISTRATIVE AND REGULATORY

Multicenter Management and Coordination

The YCCI MCU will support the Sponsor-Investigator with the multi-site management aspects of this trial. This includes, but is not limited to, study start-up, regulatory assistance (IRB submissions, amendments, and renewals), provision of template study forms (tracking and eligibility checklists, etc.), site qualification and activation, training, and overall project management. The MCU will provide tools to assist the study teams in conducting the trial appropriately and according to Good Clinical Practice Standards.

The MCU will ensure that all participating sites undergo remote training in which all key study personnel will be instructed study procedures, informed consent, source documentation requirements, safety and adverse event reporting, Good Clinical Practice guidelines and additional study related topics. This training will be conducted by the YCCI Study Monitor and/or MCU staff and documentation of completion will be required for all personnel.

Data and Safety Monitoring Committee

The Yale Cancer Center (YCC) Data and Safety Monitoring Committee (DSMC) will provide the primary oversight of data and safety monitoring. The Yale DSMC will review and monitor compliance, toxicity and deviations from this study. The committee is composed of clinical specialists with experience in oncology and who have no direct relationship with the study. Information that raises any questions about participant safety will be addressed with the Principal Investigator.

The DSMC will review this protocol bi-annually, at a minimum. Information to be provided to the committee includes: a study narrative by the PI, a summary DSMC report produced by OnCore (which includes participant accrual, response, trial status history, SAEs, adverse events, deviations and survival); audit results, and monitoring reports, as applicable. Other information (e.g., scans, laboratory values, etc.) will be provided upon request. Upon completing the review, the DSMC will approve whether the study should continue as planned, require modification/ amendment, or be placed on administrative hold with accrual temporarily suspended.

Trials being monitored by the YCC DSMC will remain under the YCC DSMC purview until a DSMC review has occurred that includes the research activity of the last subject who completed the intervention, or until the DSMC feels there are no patient safety concerns that require further monitoring. The DSMC will determine the length of continued DSMC review.

The DSMC has authority to intervene in the conduct of these studies as necessary to ensure the safety of the participants and to maintain the highest quality in the clinical research performed at YCC. The DSMC has the authority to require additional monitoring and/ or more frequent reporting on study progress and serious adverse events.

Study Site Monitoring

Study site monitoring is necessary to assure adequate protection of the rights of human subjects and the safety of all subjects involved in clinical investigations and the quality and integrity of the resulting data submitted.

The Sponsor-Investigator-designated monitor(s) conducts monitoring visits to ensure that clinical investigators and study team members are compliant with the protocol, ICH good clinical practice, federal, state and local regulations and institutional policies and procedures, that data are of high quality and integrity, and that the facilities and staffing are adequate for continued study participation. This will be performed by conducting monitoring visits including a site initiation visit, regularly scheduled interim monitoring visits and/or remote interim monitoring visits while subjects are on study, and a site close-out visit at all participating sites. Following each site visit, a visit report will be generated containing information on site activities and a summary of pertinent points and action items. The report will be provided with a follow-up letter. Site-specific data status reports will be distributed to the site regularly to outline planned, missing or incomplete case report forms and any outstanding data queries.

During monitoring visits, the following may be reviewed:

- Protection of the rights, safety and welfare of subjects through review of informed consent process and documentation, adverse events (AEs) and serious adverse events (SAEs) and safety procedures
- Subject eligibility
- Source verification
- Protocol compliance
- Deviations and Non-compliance
- Investigator Site File
- GCP compliance
- If applicable, include: Investigational Drug/ Device Storage and Accountability (including quantity and disposal procedures)
- If applicable, include: Laboratory Facilities
- If applicable, include: Equipment maintenance and calibration
- Additional study supplies inventory and assessment
- Study progress and/or follow-up on issues with Site Principal Investigator (PI) and relevant members of the study team

The Sponsor-Investigator and YCCI will define the required study monitoring activities in a Study Monitoring Plan.

DATA HANDLING AND RECORD KEEPING

As used in this protocol, the term CRF should be understood to refer to either a paper form or an electronic data record or both, depending on the data collection method used in this study.

A CRF is required and should be completed for each included patient. The investigator has ultimate responsibility for the collection and reporting of all clinical, safety and laboratory data entered on the CRFs and any other data collection forms (source documents) and ensuring that they are accurate, authentic/original, attributable, complete, consistent, legible, timely (contemporaneous), enduring and available when required. Any corrections to entries made in the CRFs or source documents must be dated, initialed and explained (if necessary) and should not obscure the original entry. In most cases, the source documents are the hospital's or the physician's patient chart. In these cases, data collected on the CRFs must match the data in those charts.

In some cases, the CRF, or part of the CRF, may also serve as source documents. The investigators are required to prepare and maintain adequate and accurate case histories designed to record all observations and other data pertinent to the investigation on each individual treated in the investigation. Data that are derived from source documents and reported on the CRF must be consistent with the source documents or the discrepancies must be explained. Forte EDC will be the designated electronic data capture tool. All data should be entered onto the EDC System within 1 week of study entry. AEs need to be entered within 72 hours and SAEs need to be entered within 24 hours of the site becoming aware of the event.

CONFIDENTIALITY & SECURITY OF DATA

Data will be entered into the Electronic Data Capture (EDC) System. De-identified data will then be downloaded in Excel format for statistical analysis, which will be done on a HIPAA compatible, password protected encrypted laptop computer. All data entry will be performed by the local study site personnel. All source documentation will be retained at the local study site per local site regulations and monitored during regularly scheduled monitoring visits.

Record Retention

To enable evaluations and/or audits from regulatory authorities or Yale, the investigator agrees to keep records, including the identity of all participating patients (sufficient information to link records, e.g. CRFs and hospital records), all original signed informed consent/assent documents, copies of all CRFs, safety reporting forms, source documents, and detailed records of treatment disposition, and adequate documentation of relevant correspondence (e.g. letters, meeting minutes, and telephone call reports). The records should be retained by the investigator according to International Conference on Harmonization (ICH), according to local regulations, or as specified in the clinical study agreement (CSA), whichever is longer.

If the investigator becomes unable for any reason to continue to retain study records for the required period (e.g., retirement, relocation), Yale should be prospectively notified.

ETHICS

This study will be conducted in accordance with the consensus ethical principles derived from international guidelines including the Declaration of Helsinki; applicable Good Clinical Practice (GCP) Guidelines published by the International Conference on Harmonisation; and applicable US laws and regulations including those found in 21 CFR Parts 50, 54, 56, and 312.

Institutional Review Board (IRB)

It is the responsibility of the investigator to have prospective approval of the study protocol, protocol amendments, informed consent/assent documents, and other relevant documents, e.g. recruitment advertisements, if applicable, from the IRB. All correspondence with the IRB should be retained in the investigator file. Copies of IRB approvals should be forwarded to the Project Manager.

The only circumstance in which an amendment may be initiated prior to IRB approval is where the change is necessary to eliminate apparent immediate hazards to the patients.

Financial Disclosure

Investigators and sub-investigators will provide the Sponsor PI with sufficient, accurate financial information as requested to allow the sponsor to submit complete and accurate financial certification or disclosure statements to the appropriate regulatory authorities. Investigators are responsible for providing information on financial interests during the course of the study and for 1 year after completion of the study.

